8.0 Efficacy Analyses

8.1 General Considerations

Unless otherwise specified, all randomized subjects in the ITT population will be included in the efficacy analyses. All statistical tests will be 2-sided at an alpha level of 0.05.

The primary analysis will be performed after all ongoing subjects have completed 24 weeks of follow-up and the database has been locked. Unless otherwise specified, data after the cutoff date will be excluded from statistical analyses.

Unless otherwise specified, all subjects will be analyzed according to the baseline platelet count and DIPSS+ score collected in Electronic Data Capture (EDC) system. For subjects with missing karyotype information, the DIPSS+ score will be calculated by assuming these subjects do not have unfavorable karyotype. The DIPSS+ score will be categorized by intermediate (including both intermediate-1 and intermediate-2) and high risk.

Unless otherwise specified, binary variables (e.g., response rates) will be analyzed using Cochran-Mantel-Haenszel (CMH) test, stratified by DIPSS+ risk group (intermediate versus high risk) and platelet count ($\leq 200 \times 10^9/L$ versus $> 200 \times 10^9/L$). The 95% confidence interval for the response rate will be provided for each treatment arm using the exact binomial distribution. The strata-adjusted difference in the response rates between the treatment arms and the 95% confidence interval for the difference will also be provided.

Unless otherwise specified, continuous data from patient-reported outcome will be analyzed using linear mixed effects model with treatment arm, visit, treatment by visit interaction, DIPSS+ risk group (intermediate versus high risk), platelet count ($\leq 200 \times 10^9/L$ versus $> 200 \times 10^9/L$) and baseline score as fixed effects. An unstructured variance covariance matrix will be used. The compound symmetry variance covariance matrix will be used if the model does not converge with the unstructured matrix. Change in score from baseline will be compared between the treatment arms for the specified post-baseline visit. The least-squares mean change from baseline and the corresponding 95% confidence interval will be provided for each treatment arm. In addition, the least-squares mean of the difference between the treatment arms and the corresponding 95% confidence interval will be provided.

Unless otherwise specified, time-to-event endpoints will be analyzed using Kaplan-Meier methodology and compared between treatment arms using the log-rank test, stratified by DIPSS+ risk group (intermediate versus high risk) and platelet count ($\leq 200 \times 10^9/L$ versus $> 200 \times 10^9/L$). The hazard ratio between treatment arms and the corresponding 95% confidence interval will be estimated using the Cox proportional hazards model, stratified by DIPSS+ risk group (intermediate versus high risk) and platelet count ($\leq 200 \times 10^9/L$ versus $> 200 \times 10^9/L$).

Unless otherwise specified, if a subject prematurely breaks the blind, data after the blind break will be included in the statistical analysis as appropriate based on the definition and analysis of the efficacy endpoints.

Unless otherwise specified, baseline refers to the last non-missing observation before the first administration of study drug or randomization if no study drug is given.

Unless otherwise specified, a confirmed disease progression is defined as any of the following:

- Two consecutive disease responses of progressive disease or relapse, in which case the date of the confirmed disease progression will be the date of the first progressive disease or relapse

- A progressive disease due to leukemic transformation
- A progressive disease or relapse that is the last disease response of a subject.

At the time this SAP is written, the evidence-based MCT for change from baseline in TSS at Week 24 is determined to be –10.

8.2 Handling of Missing Data

Unless otherwise specified, missing data will be analyzed using the following methods for the efficacy analyses:

- Binary variables: If a subject does not have evaluation during a specific visit window, the subject will be considered a non-responder for that visit.
- Continuous variables: Mixed-effect Model Repeat Measurement (MMRM) will be used as the primary approach for handling missing data. Parameter estimation in linear mixed effects models will be based on the assumption of data being missing at random and the method of restrictive maximum likelihood (REML).
- Time-to-event variables: The time-to-event analysis will be based on observed data and will not impute values for missing evaluations. Subjects who do not have the event of interest will be censored at the censoring date defined for the respective endpoint in Section 8.3, Section 8.4 and Section 8.5.

Tipping Point Analysis for Binary Variables

The tipping point analyses will be performed to assess the robustness of the primary analysis results for SVR_{35W24} and TSS_{50W24} under missing not at random assumptions. The tipping point analyses are two-dimensional (i.e., assumptions about the missing outcomes on the treatment arm and the placebo arm can vary independently). The response rate among those subjects with a missing response is assumed to be p_0 for the control arm and p_1 for the treatment arm, and the response rate p_0 and p_1 systematically vary from 0% to 100% by every 10%, respectively. Given a set of (p_0, p_1) , the subjects with a missing response will be randomly assigned as responders or non-responders using

binomial distribution to generate 30 imputed datasets, and the same CMH method used for the primary analysis will be performed on each of the multiple imputed datasets to obtain the results for each comparison of the treatment arm versus the control arm. These results will then be aggregated using Rubin's method.

If one pair of shift parameters is found to just reverse the study conclusion (two-sided p -value > 0.05), then the shift parameters are identified as the tipping point. The results for a grid of shift parameter combinations are tabulated.

Tipping Point Analysis for Continuous Variables

The tipping point analyses will be conducted as a two-dimensional sensitivity analysis to check the departure from the MAR assumption on the treatment arm and the control arm independently. The focused scenarios are when missing outcomes on the treatment arm are worse than the imputed values using the MAR assumption on the treatment arm, while missing outcomes on the control arm are better than the imputed values using the MAR assumption on the control arm. In each treatment group, missing values will be first imputed via MI under MAR assumption using observed data, and then a shift parameter will be added to the imputed values. A different shift parameter may be specified for each treatment group and be implemented by PROC MI using the missing not at random (MNAR) statement. The imputation uses a two-step approach, an augmentation step using Markov Chain Monte Carlo (MCMC) and an imputation step using Monotone Regression. The MNAR statement is applied in the imputation step. The number of imputed datasets is 30. For TSS at Week 24, the imputation model will include DIPSS+ risk group (intermediate versus high risk), platelet count ($\leq 200 \times 10^9/L$ versus $> 200 \times 10^9/L$), and TSS scores at baseline, Week 8 and Week 12. For PROMIS Fatigue score at Week 24 and physical functioning score at Week 24, the imputation model will include DIPSS+ risk group (intermediate versus high risk), platelet count ($\leq 200 \times 10^9/L$ versus $> 200 \times 10^9/L$), and TSS scores at baseline, Week 4 and Week 12.

In cases where the shifted values have exceeded the maximum value of the endpoint (i.e., out of range), the minimum or maximum value of the endpoint will be used in

further analysis steps. For each pair of shift values, ANCOVA model using PROC MIXED will be performed on each imputed dataset for a pairwise comparison between treatment and control arms. ANCOVA model will include the fixed effects of treatment, stratification factors, and the baseline score. Analysis results from each imputed dataset will be aggregated using Rubin's method.

If one pair of shift parameters is found to reverse the study conclusion (two-sided p -value > 0.05), then the shift parameters are identified as the tipping point. The results for a grid of shift parameter combinations will be tabulated.

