APPENDIX D. ACTIVITY SCHEDULE

The following table shows the required activities. The individual activities are described in detail in the **Operations Manual**.

Study Activities Table

Activity	Screening/ Baseline	Week 1	Week 1	Week 2	Week 3	Week 5	Week 7	Week 9	Week 13, 17, 21, 25	Q12 weeks as of Week 37	Treatment Completion Visit	30-Day Safety Visit (± 3 Days)	Post-Treatment Visits (± 3 Weeks)	Survival Follow Up
	Day -28 to Day -1	Day 1	Day 2	Day 1 (± 1 day)	Week 13, 17, 21 Day 1 (± 2 days). Week 25 Day 1 (± 3 days)	From Week 37 Day 1 (± 4 days)								
INTERVIEWS & QUESTIONNAIRES														
Informed consent	✓													
Eligibility criteria	✓													
Medical/surgical/transfusion history	✓	✓												
Alcohol and nicotine use	✓													
Adverse event assessment	✓	✓	✓	✓	✓	✓	✓	✓	✓	✓	✓	✓		
Prior/concomitant therapy/transfusion	✓	✓	✓	✓	✓	✓	✓	✓	✓	✓	✓			
Post-treatment therapy/transfusion/surgery												✓	✓	✓
MFSAF v4.0 (Daily)	✓	✓ (Daily through end of Week 36)												
EORTC QLQ-C30 v3.0		✓				✓			✓ (Week 13, 25)	✓	✓			
PROMIS Fatigue SF 7a	✓	✓				✓			✓ (Week 13, 25)	✓	✓			
EQ-5D-5L		✓				✓			✓ (Week 13, 25)	✓	✓			
PGIC									✓ (Week 13, 25)					

Activity	Screening/ Baseline	Week 1	Week 1	Week 2	Week 3	Week 5	Week 7	Week 9	Week 13, 17, 21, 25	Q12 weeks as of Week 37	Treatment Completion Visit	30-Day Safety Visit (± 3 Days)	Post-Treatment Visits (± 3 Weeks)	Survival Follow Up
	Day -28 to Day -1	Day 1	Day 2	Day 1 (± 1 day)	Week 13, 17, 21 Day 1 (± 2 days). Week 25 Day 1 (± 3 days)	From Week 37 Day 1 (± 4 days)								
PGIS	✓	✓							✓ (Week 13, 25)					
ECOG performance status	✓	✓		✓	✓	✓	✓	✓	✓	✓	✓			
Survival follow-up call (approximately every 2 months for up to 8 years)														✓
LOCAL LABS & EXAMS														
MRI (or CT scan) for spleen assessment	✓								✓ (Week 13, 25)	✓ (Week 37, 49, 73, 97)	✓		✓	
12-lead ECG	✓					✓					✓			
Vital signs: including height (Screening only), weight, BP, pulse, and body temperature	✓	✓		✓	✓	✓	✓	✓	✓	✓	✓	✓		
Physical examination including skin examination, spleen and liver measurement by palpation	✓	✓		✓	✓	✓	✓	✓	✓	✓	✓		✓	
Disease Assessment by IWG									✓ (Week 13, 25)	✓ (Week 37, 49, 73, 97)	✓		✓	
Serum/urine pregnancy test	✓	✓				✓		✓	✓ (monthly from Week 25 where a	✓ (monthly where a regulatory requirement)	✓			

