8.4.1.2 At Least 35% Reduction in Spleen Volume from Baseline (SVR₃₅)

SVR₃₅ rate is defined as the proportion of subjects who achieve at least 35% reduction in spleen volume from baseline at any time during the study. Subjects who do not have any post-baseline spleen volume assessment or who have had confirmed disease progression or started post-study treatment prior to achieving SVR₃₅ will be treated as non-responders. Subjects who do not receive any study drug will be treated as non-responders. Subjects

without baseline spleen volume assessment or with unevaluable baseline spleen volume will be treated as non-responders.

SVR₃₅ rate will be analyzed using the statistical method described for binary variables in Section 8.1. In addition, descriptive summaries of spleen volume and percent change from baseline at each visit will be provided for each treatment arm and will be presented graphically. Maximum percent reduction from baseline will also be presented graphically for each treatment arm. Time to first SVR₃₅ will be descriptively summarized for each treatment arm. The proportion of subjects who achieve at least 35% reduction in spleen volume from baseline at Week 12 will be descriptively summarized for each treatment arm.

8.4.1.3 Change in Fatigue from Baseline at Week 24

Patient reported outcome on fatigue will be assessed using the global fatigue score as measured by PROMIS Cancer Fatigue SF 7a.⁴ Scores will be computed according to the PROMIS Cancer Fatigue SF 7a scoring manual. All questions must be answered to calculate the total score. Change in scores from baseline at Week 24 will be compared between the treatment arms using the linear mixed effects model described in Section 8.1. The tipping point analysis described in Section 8.2 will be performed as sensitivity analyses. T-scores will be used in the analysis.

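### The tipping-point imputation for Week 24 fatigue and physical functioning is built on TSS scores instead of the endpoint's own scores, so its zero-shift point is not the main MAR result

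*SAP*

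**What the plan says.** **Main analysis.** SAP 8.4.1.3 (fatigue) and 8.4.1.5 (physical functioning) use the linear mixed model of SAP 8.1. Its terms are arm, visit, their interaction, DIPSS+ group, platelet group "and baseline score as fixed effects", with an unstructured covariance across the endpoint's visits. TSS is not a term. SAP 8.2 states the missing-data approach: "Mixed-effect Model Repeat Measurement (MMRM) will be used as the primary approach for handling missing data", under MAR.

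**Sensitivity analysis.** Both sections then say: "The tipping point analysis described in Section 8.2 will be performed as sensitivity analyses". In SAP 8.2, missing values are imputed by arm under MAR, "and then a shift parameter will be added to the imputed values", and each completed dataset goes to an ANCOVA: "ANCOVA model will include the fixed effects of treatment, stratification factors, and the baseline score".

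**Imputation models.** SAP 8.2 gives two. For TSS at Week 24, the predictors are the two strata and TSS at baseline, Week 8 and Week 12, which are the endpoint's own scores. For the other two endpoints it reads "For PROMIS Fatigue score at Week 24 and physical functioning score at Week 24, the imputation model will include" the same strata and "TSS scores at baseline, Week 4 and Week 12". No PROMIS or QLQ-C30 score is listed.

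**Schedule.** Protocol Appendix D collects "PROMIS Fatigue SF 7a" and the QLQ-C30 on Day 1 of Weeks 1, 5, 13 and 25, that is, at baseline and after 4, 12 and 24 weeks.

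**The concern.** A tipping-point analysis asks how far the missing outcomes must move from their MAR values before the conclusion changes. That distance can be interpreted only if the unshifted grid point corresponds to the main MAR analysis. MAR given TSS history is a different assumption from MAR given the endpoint's own history. If dropout depends on a subject's fatigue score, the mixed model accounts for this through the observed fatigue scores, whereas an imputation from TSS does so only as far as TSS tracks fatigue.

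The imputation model also omits the baseline score used in the ANCOVA. Imputed values are then linked to that baseline only through TSS, and the pooled baseline slope is attenuated.

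At stake is whether the robustness statement for these two endpoints can be relied on. Depending on the dropout pattern, the grid could start too favourably and make the result look sturdier than it is, or too unfavourably and make it look fragile.

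**Working it through.** The plan gives no figure to reproduce. The defect is shown by comparing what each model conditions on; its size can only be illustrated.

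**1. Conditioning sets**

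| Step | Strata | Endpoint's own baseline | Endpoint's own Weeks 4, 12 | TSS |
|---|---|---|---|---|
| Mixed model (8.1) | yes | yes | yes | no |
| Imputation (8.2) | yes | not listed | not listed | baseline, Weeks 4, 12 |
| ANCOVA after imputation (8.2) | yes | yes | no | no |

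**2. Assumptions (none are in the documents)**
- Correlation between visits within an instrument: r = 0.6 to 0.7.
- Same-visit correlation of TSS with the endpoint: c = 0.5 to 0.7.
- Cross-instrument, cross-visit correlation: c × r.

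**3. Week 24 variance explained by three earlier scores**
- Own scores: 3r²/(1+2r). For r = 0.6, 1.08/2.2 = 0.49; for r = 0.7, 1.47/2.4 = 0.61.
- TSS scores: c² times that. Lowest 0.25 × 0.49 = 0.12; highest 0.49 × 0.61 = 0.30.

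**4. One subject's prediction.** Take a subject 10 T-score points (1 SD) worse at Weeks 4 and 12, with an average own baseline and TSS at the values expected from the own scores.
- Own scores predict 2 × 10 × r/(1+2r) points worse at Week 24: 12/2.2 = 5.5 for r = 0.6 and 14/2.4 = 5.8 for r = 0.7.
- TSS predicts c² times that: 0.25 × 5.5 = 1.4 up to 0.49 × 5.8 = 2.9 (2.86 before rounding).
- The gap is (1 − c²) times the own-score prediction: 0.51 × 5.45 = 2.8 to 0.75 × 5.83 = 4.4 points.

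**5. Treatment difference at zero shift.** This is a large-sample simulation with a 0.40 SD benefit on both instruments at Weeks 4, 12 and 24. Dropout is logistic in the own Week 12 score (log-odds 1 per SD) with 20–30% missing. Imputation is by arm, followed by ANCOVA on treatment and own baseline.

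| Dropout pattern | Own-score imputation | TSS imputation |
|---|---|---|
| (a) Same rule in both arms | 0.40 | 0.37–0.39 |
| (b) Worse scorers leave Arm A; Arm B unrelated to score | 0.40 | 0.46–0.54 |
| (c) Worse scorers leave Arm B; Arm A unrelated to score | 0.40 | 0.26–0.34 |

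In (a) the small shift arises because treatment benefit makes the arms' missing rates differ; with equal rates it vanishes. The pooled baseline slope falls from 0.60 to about 0.44–0.53, or from 0.70 to about 0.50–0.62.

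For scale, the complete-data ANCOVA standard error at 115 per arm is √[(2/115)(1 − r²)]: 0.11 SD for r = 0.6 and 0.09 SD for r = 0.7.

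**6. Check against a fitted mixed model.** This used SD 10, r = 0.7, a true difference of −3 points, c from 0.3 to 0.7, and score-dependent dropout in the navitoclax arm only (13–38% missing there, 10–20% in control). The strata were left out.
- Large-sample estimates: mixed model −2.8 to −3.2; own-score imputation −2.8 to −3.2 (within 0.08 of the mixed model); TSS imputation −3.4 to −4.9 (0.4 to 2.0 points away).
- Mean absolute gap from the mixed model at 115 per arm: 0.07–0.20 points with own scores, 0.43–1.86 with TSS.

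**The case against.** **It is probably a slip.** The Week 4 and Week 12 times match the questionnaires' visits, while the TSS model uses Weeks 8 and 12; the phrase looks carried over from the preceding sentence. A list of what a model will include also does not forbid other predictors, so a programmer might use the right scores. This is likely true, but nothing in either document corrects the phrase, and a prespecified model should name its essential predictors, as the TSS sentence does.

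**Exact agreement is too strict a test.** Imputation plus ANCOVA never equals a mixed model exactly, and the TSS tipping model uses fewer visits than its own main model, which takes weekly scores up to Week 24 (SAP 8.4.1.1). Correct, but the TSS model does condition on the endpoint's own history. With own scores the gap in step 6 is small.

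**The size is assumed.** This stands. The larger shifts need score-dependent dropout in one arm only, and their direction reverses with the arm. Protocol 2.2 names thrombocytopenia as navitoclax's primary dose-limiting toxicity. That makes unequal discontinuation plausible but does not show that it depends on fatigue or function. TSS contains a fatigue item, so c could exceed 0.7; at c = 0.8 and 20% missing, the shift in (b) is about 0.04–0.05 SD. The simulation in step 5 also assumes that Week 4 and Week 12 scores are always observed, which favours own-score imputation. The point figures are on the T-score scale and do not carry over to QLQ-C30.

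**The reach is limited.** This also stands. The endpoints are eighth and ninth in SAP Table 1, and no claim on them is possible until everything above, including OS and LFS, has succeeded.

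**Conclusion.** The concern holds. As written, the imputation for these two endpoints omits their own scores, conditions on a different instrument, and leaves out the baseline that its own ANCOVA uses. The grid still explores departures from MAR, but from a displaced origin, so the tipping distance is not a distance from the mixed-model estimate.

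The displacement cannot be sized from the documents. Under the stated assumptions it is 0.01–0.03 SD with a common dropout rule and 0.06–0.14 SD with one-arm score-dependent dropout, in either direction. The upper end is comparable with the standard error of the treatment difference; with no missing Week 24 scores it is zero. The main tests of these endpoints, the primary endpoint and the alpha hierarchy are untouched. It should be corrected because the repair is nearly free, not because it threatens the trial's main conclusions.

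**What to change.** In SAP 8.2, rewrite the predictor list for these endpoints:
- Fatigue at Week 24: the two strata and PROMIS Fatigue T-scores at baseline, Week 4 and Week 12.
- Physical functioning at Week 24: the two strata and QLQ-C30 physical functioning scores at baseline, Week 4 and Week 12.
- TSS at those visits may stay as an optional auxiliary predictor, in addition to the own scores.

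Add that the zero-shift result will be tabulated beside the mixed-model estimate and its confidence interval for each endpoint, so that the reader can confirm where the grid starts.

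The cost is one phrase and one reporting sentence in the SAP, and a change of input variables in PROC MI. The scores are already scheduled at these visits, so no new data are needed.

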8.3 Primary Efficacy Endpoint(s) and Analyses

8.3.1 Primary Efficacy Endpoint(s)

The primary efficacy endpoint is at least 35% reduction in spleen volume at Week 24 (SVR_{35W24}) from baseline as measured by magnetic resonance imaging (MRI) or computed tomography (CT) scan and assessed centrally, per International Working Group (IWG) criteria.²

8.3.2 Handling of Missing Data for the Primary Efficacy Endpoint(s)

The analysis window for Week 24 is defined as from [REDACTED] per study activity schedule with consideration of COVID-19 related interruptions. Subjects who do not have spleen volume assessment in the analysis window will be treated as non-responders. Subjects who do not receive any study drug will be treated as non-responders. Subjects without baseline spleen volume assessment or with unevaluable baseline spleen volume will be treated as non-responders. Spleen volume assessments after confirmed disease progression or start of post-study treatment will not be included in the analysis.

8.3.3 Primary Efficacy Analysis

The proportion of subjects who achieve SVR_{35W24} will be compared between the treatment arms using Cochran-Mantel-Haenszel (CMH) test, stratified by DIPSS+ risk group (intermediate versus high risk) and platelet count ($\leq 200 \times 10^9/L$ versus $> 200 \times 10^9/L$). The DIPSS+ risk group collected in EDC and the baseline platelet count collected in EDC will be used in the primary efficacy analysis as described in Section 8.1. The 95% confidence interval for the SVR_{35W24} rate will be provided for each treatment arm using the exact binomial distribution.

8.3.4 Additional Analyses of the Primary Efficacy Endpoint(s)

The following additional analyses will be performed for SVR_{35W24}:

- Percent change from baseline in spleen volume at Week 24 will be summarized for each treatment arm and presented graphically in waterfall plots.
- Sensitivity analysis of SVR_{35W24} will be performed by excluding subjects whose DIPSS+ risk group is intermediate-1.
- Spleen volume reduction at Week 24 will be descriptively summarized by the following categories: $\geq 10\%$ to $< 25\%$, $\geq 25\%$ to $< 35\%$, $\geq 35\%$ to $< 50\%$, and $\geq 50\%$.
- CMH test stratified by DIPSS+ risk group (intermediate-2 versus high risk) and platelet count ($\leq 200 \times 10^9/L$ versus $> 200 \times 10^9/L$) collected in IRT.
- Tipping point analysis as described in Section 8.2.

Logistic regression with model selection procedure using relevant demographic and baseline characteristics in Section 7.1 may be performed to evaluate the robustness of the primary analysis.

